#### 8.2.4. Clinical Safety Laboratory Assessments

Blood samples for serum chemistry and hematology and a random urine sample for urinalysis will be collected as noted in Section 10.2, [Appendix 2: Clinical Laboratory Tests](#). The investigator must review the laboratory results, document this review, and record any clinically relevant changes occurring during the study in the adverse event section of the eCRF. The laboratory reports must be filed with the source documents. The data of local laboratory test except for HBsAg and HCV antibody test and HIV test at screening must be recorded in eCRF.

#### 8.2.5. Pregnancy Testing

Additional serum or urine pregnancy tests may be performed, as determined necessary by the investigator or required by local regulation, to establish the absence of pregnancy at any time during the participation in the study.

#### 8.2.6. Management of Common Expected Toxicities

For participants with AST and/or ALT elevations, pancreatic amylase elevation, gastrointestinal system toxicities, musculoskeletal system and cardiac muscle toxicities, and cardiac rhythm disturbances, the following should be done (refer Section 10.7, [Appendix 7: A Division of Microbiology and Infectious Diseases \(DMID\) Adult Toxicity Table \(November 2007\)](#)).

##### ***AST and/or ALT Elevation***

$<5.0 \times$  ULN AST or ALT elevation with normal bilirubin:

Participants may continue to take the study intervention. Participants should be followed until resolution (return to baseline) or stabilization of AST/ALT elevation. Clinical symptoms, AST,

ALT, and serum bilirubin should be monitored every 2 weeks until clinically stable as necessary to manage the participant's condition.

$\geq 5.0 \times \text{ULN}$  but  $\leq 8.0 \times \text{ULN}$  AST or ALT elevation or  $\geq 3 \text{ ULN}$  accompanied by bilirubin  $\geq 2.0 \times \text{ULN}$ :

Participants will be permanently discontinued from treatment of the suspected causative background agent or temporarily withhold study intervention at the investigator's discretion. Clinical symptoms, AST, ALT, and serum bilirubin should be monitored every 2 weeks until clinically stable as necessary to manage the participant's condition. If ALT, AST, and bilirubin do not improve or worsens within 2 weeks, the study intervention will be temporarily withheld for up to 2 weeks per investigator discretion. Additional tests should be performed to evaluate the cause of hepatitis (eg, hepatitis A, B, C). Liver enzymes, including serum bilirubin should be monitored as frequently as necessary to manage the participant's condition. If AST/ALT decreases to  $< 5.0 \times \text{ULN}$ , study intervention can be restarted once. Participants who fail to show improvement, demonstrated by no improvement in clinical course or persistent AST and ALT  $\geq 5.0 \times \text{ULN}$  values, or persistent AST/ALT  $\geq 3.0 \times \text{ULN}$  accompanied by bilirubin  $\geq 2.0 \times \text{ULN}$  (over 4 weeks) will have to permanently discontinue the study intervention. Participants should be followed until resolution or stabilization (return to baseline) of AST/ALT/bilirubin elevation.

$> 8.0 \times \text{ULN}$  AST or ALT elevation

Per investigator discretion, the study intervention will be temporarily withheld for up to 2 weeks. Additional tests should be performed to evaluate the cause of hepatitis (eg, hepatitis A, B, C). Liver enzymes, including serum bilirubin should be monitored as frequently as necessary to manage the participant's condition. If AST/ALT decreases to  $< 5.0 \times \text{ULN}$ , study intervention can be restarted one time. Participants who fail to show improvement, demonstrated by no improvement in clinical course or persistent AST and ALT  $\geq 5.0 \times \text{ULN}$  values, or persistent AST/ALT  $\geq 3 \times \text{ULN}$  accompanied by bilirubin  $\geq 2.0 \times \text{ULN}$  will have to permanently discontinue the study intervention but can continue the study procedures. Participants should be followed until resolution or stabilization (return to baseline) of AST/ALT elevation.

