### **5.6.3. Additional Safety Assessments**

#### **5.6.3.1. Clinical Laboratory Tests**

Clinical laboratory tests will be displayed for the participants included in the safety analysis set.

Descriptive statistics (n, mean, SD, minimum, median and maximum) and graphical displays will be presented for chemistry, hematology, and urinalysis laboratory tests at scheduled time points by intervention arm and study phase.

Change/percent change from baseline to each scheduled time point will be summarized for chemistry, hematology, and urinalysis tests and displayed by intervention group.

An abnormality (toxicity grade and/or abnormality based on normal ranges) will be attributed to the baseline and postbaseline values.

Postbaseline abnormalities will be compared with their corresponding baseline result:

- For toxicity grades, treatment emergent (TE) will be concluded if the postbaseline value is worse than the baseline value.
- For abnormalities based on normal range and/or criteria: If the postbaseline value is above the upper limit and the baseline value is below the upper limit (eg, Normal or Low), then the postbaseline abnormality will be considered TE. The same applies to the postbaseline value being below the lower limit with the baseline value being above the lower limit (eg, Normal or High).
- If the baseline value is missing, a postbaseline abnormality will always be considered as TE.

Number and percentage of participants with clinically important laboratory values and/or markedly abnormal values (defined as grade 3 or higher) will be presented by intervention group over time. Listing of clinically important laboratory values will be defined according to DMID definitions.

Plots of mean (+/-SE) values and changes from baseline over time for clinically important laboratory parameters will be presented by intervention arm and analysis phase.

Shift tables will be provided summarizing the shift in laboratory values from baseline over time with respect to abnormality criteria (low, normal, high).

Descriptive statistics by toxicity grade over time will be presented. Shift summaries from baseline toxicity grade to the worst toxicity grade will also be presented.

Shift summaries from baseline laboratory value to the worst grade in chemistry and hematology tests will be presented.

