**6.10. Appendix 10 Laboratory Toxicity Grading**

The grading scale use for lab assessments is based on DMID and defined as follows.

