**Chemistry**

	Grade 1	Grade 2	Grade 3	Grade 4
Hyponatremia	130 - 135 mEq/L	123 - 129 mEq/L	116 - 122 mEq/L	<116 mEq/L
Hypernatremia	146 - 150 mEq/L	151 - 157 mEq/L	158 - 165 mEq/L	>165 mEq/L
Hypokalemia	3.0 - 3.4 mEq/L	2.5 - 2.9 mEq/L	2.0 - 2.4 mEq/L	<2.0 mEq/L
Hyperkalemia	5.6 - 6.0 mEq/L	6.1 - 6.5 mEq/L	6.6 - 7.0 mEq/L	>7.0 mEq/L
Hypoglycemia	55 - 64 mg/dL	40 - 54 mg/dL	30 - 39 mg/dL	<30 mg/dL
Hyperglycemia (nonfasting and no prior diabetes)	116 - 160 mg/dL	161 - 250 mg/dL	251 - 500 mg/dL	>500 mg/dL
Hypocalcemia (corrected for albumin)	8.4 - 7.8 mg/dL	7.7 - 7.0 mg/dL	6.9 - 6.1 mg/dL	<6.1 mg/dL
Hypercalcemia (correct for albumin)	10.6 - 11.5 mg/dL	11.6 - 12.5 mg/dL	12.6 - 13.5 mg/dL	>13.5 mg/dL
Hypomagnesemia	1.4 - 1.2 mEq/L	1.1 - 0.9 mEq/L	0.8 - 0.6 mEq/L	<0.6 mEq/L
Hypophosphatemia	2.0 - 2.4 mg/dL	1.5 - 1.9 mg/dL	1.0 - 1.4 mg/dL	<1.0 mg/dL

	Grade 1	Grade 2	Grade 3	Grade 4
Hyperbilirubinemia (with Grade 1 or more AST, ALT or ALP)	1.1 - <1.25 x ULN	1.25 - <1.5 x ULN	1.5 – 1.75 x ULN	>1.75 x ULN
Hyperbilirubinemia (with normal AST, ALT and ALP)	1.1 - <1.5 x ULN	1.5 - <2.0 x ULN	2.0 - 3.0 x ULN	>3.0 x ULN
Blood urea nitrogen (BUN)	1.25 - 2.5 x ULN	2.6 - 5 x ULN	5.1 - 10 x ULN	>10 x ULN
Hyperuricemia (uric acid)	7.5 - 10.0 mg/dL	10.1 - 12.0 mg/dL	12.1 - 15.0 mg/dL	>15.0 mg/dL
Creatinine	1.1 - 1.5 x ULN	1.6 - 3.0 x ULN	3.1 - 6 x ULN	>6 x ULN
AST (SGOT)	1.1 - <2.0 x ULN	2.0 - <3.0 x ULN	3.0 - 8.0 x ULN	>8 x ULN
ALT (SGPT)	1.1 - <2.0 x ULN	2.0 - <3.0 x ULN	3.0 - 8.0 x ULN	>8 x ULN
GGT	1.1 - <2.0 x ULN	2.0 - <3.0 x ULN	3.0 - 8.0 x ULN	>8 x ULN
Alkaline Phosphatase	1.1 - <2.0 x ULN	2.0 - <3.0 x ULN	3.0 - 8.0 x ULN	>8 x ULN
Amylase	1.1 - 1.5 x ULN	1.6 - 2.0 x ULN	2.1 - 5.0 x ULN	>5.1 x ULN

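### The second liver tier in Section 8.2.6 permits one restart on AST/ALT alone, so for up to about 4 weeks dosing can resume with bilirubin still at least 2.0 × ULN

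*Protocol*

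**What the plan says.** Protocol Section 8.2.6 manages AST/ALT elevation in three tiers.

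- **Below 5.0 × ULN with normal bilirubin.** Dosing may continue.
- **5.0 to 8.0 × ULN, or at least 3 × ULN with bilirubin at least 2.0 × ULN.** The first step is to stop the suspected background drug permanently "or temporarily withhold study intervention at the investigator's discretion". If enzymes and bilirubin have not improved within 2 weeks, a discretionary hold of up to 2 weeks follows. When AST/ALT is below 5.0 × ULN, "study intervention can be restarted once". A permanent stop is required for no improvement in clinical course, for persistent AST and ALT at or above 5.0 × ULN, or for persistent AST/ALT at or above 3.0 × ULN with bilirubin at or above 2.0 × ULN. The text for this last pattern ends "over 4 weeks) will have to permanently discontinue the study intervention".
- **Above 8.0 × ULN.** At the same enzyme threshold, "study intervention can be restarted one time". Participants with no improvement, or with either persistent pattern, "will have to permanently discontinue the study intervention but can continue the study procedures". No persistence period is given.

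Elsewhere, Section 7.1.1 only points back to 8.2.6. Table 3 lets bedaquiline resume after an interruption of up to 30 days and sets no liver condition. Section 7.1 requires a stop when the investigator judges it necessary for safety. Section 6.4 leaves comparator interruptions to local practice and labeling.

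SAP Appendix 10 states that "The grading scale use for lab assessments is based on DMID". Its row "Hyperbilirubinemia (with Grade 1 or more AST, ALT or ALP" grades bilirubin above 1.75 × ULN as Grade 4. AST or ALT of 3.0 to 8.0 × ULN is Grade 3. SAP Section 5.6.3.1 refers to "markedly abnormal values (defined as grade 3 or higher").

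**The concern.** In the second tier, bilirubin is part of entry, of the 2-week check, of the permanent stop and of follow-up. Restart is the one step that leaves it out. The restart sentence uses the same 5.0 × ULN limit as the first tier but drops that tier's requirement of normal bilirubin. As written, a participant who has just been taken off drug for a liver signal faces a looser test for resuming than the first tier sets for simply continuing.

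This is a patient safety matter. The protocol's background section says that bedaquiline has a signal for liver injury. Protocol Appendix 2 treats ALT at least 3 × ULN with bilirubin at least 2 × ULN (more than 35% direct) as a possible Hy's Law case that must be reported as a serious adverse event. A written restart threshold is there to guide sites in the same way through these uncommon cases, and here it points to re-dosing while the combined abnormality is unresolved.

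**Working it through.** The plan states no figure to reproduce on this point. The check sets the rules side by side, with all values in multiples of ULN.

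**Inputs**
- Tier entry (8.2.6): AST/ALT 5.0 to 8.0, or AST/ALT ≥3 with bilirubin ≥2.0.
- Restart (8.2.6): AST/ALT <5.0.
- Mandatory stop for the combined pattern (8.2.6): AST/ALT ≥3.0 with bilirubin ≥2.0, persisting over 4 weeks.
- SAP Appendix 10: AST/ALT 3.0 to 8.0 is Grade 3; bilirubin >1.75 with at least Grade 1 AST, ALT or ALP is Grade 4.

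**Step 1: overlap of restart and entry.** Restart needs AST/ALT <5.0. The second entry route needs AST/ALT ≥3 and bilirubin ≥2.0. Both hold for AST/ALT from 3 to <5 with bilirubin ≥2.0. The lowest bilirubin in the overlap exceeds the Grade 4 cut-off by 2.0 − 1.75 = 0.25, so every point is Grade 4 for bilirubin and Grade 3 for AST/ALT.

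**Step 2: how long the overlap lasts.** I took a grid in steps of 0.1. In the overlap, AST/ALT runs from 3.0 to 4.9 (20 values) and bilirubin from 2.0 to the grid limit of 5.0 (31 values), giving 20 × 31 = 620 points. Persistence was counted from onset of the abnormality, with the stop taken as reached at week 4.

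| Weeks from onset | Points meeting restart and entry, not yet stopped |
|---|---|
| 1 | 620 |
| 2 | 620 |
| 3 | 620 |
| 4 | 0 |
| 5 | 0 |

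The counts only show whether the region is open or closed. They are not frequencies of patients.

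**Step 3: which sequences reach it.** With 2 weeks of observation and then the full 2-week hold, 2 + 2 = 4 weeks have passed and the stop takes over. With a hold at onset, restart can be considered at the 2-week check, 4 − 2 = 2 weeks before the stop.

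**Step 4: worked cases**

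| Case | Current text | With the added clause |
|---|---|---|
| ALT 6 to 4, bilirubin 2.5 | Restart wording met (4 <5.0); entry still met (4 ≥3, 2.5 ≥2.0) | No restart |
| ALT 6 to 4, bilirubin normal | Restart allowed | Restart allowed |
| Enters at ALT 3.5, bilirubin 2.5 | Never at 5.0, so a fall to <5.0 sets no usable threshold | No restart until ALT <3.0 or bilirubin <2.0 |
| ALT 9 to 4, bilirubin 2.5 (above-8 tier) | Restart sentence met, but the stop clause may be met too | No restart |
| ALT 6 to 2.5, bilirubin 2.2 | Restart allowed | Restart allowed |

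Only the first row is a clear permission to restart in the combined state. The third is a missing rule. The fourth is ambiguous. The last shows the limit of the fix: bilirubin of 2.2 is still Grade 4.

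**The case against.** The strongest reply is that the restart sentence should not be read alone. The same tier provides a hold when enzymes and bilirubin have not improved by 2 weeks, and a mandatory stop for the combined pattern over 4 weeks. Restart is permissive and single. A clinical course that does not improve also ends dosing, Section 7.1 obliges the investigator to stop where safety requires it, and the IDMC monitors safety. All of this stands, and it narrows the gap. But the 2-week hold is discretionary, Section 7.1 gives no threshold, and neither says what bilirubin must be before dosing resumes.

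A second reply is that the severity markers do not isolate the defect. ALT of 4 × ULN with normal bilirubin is also Grade 3 and also fails exclusion criterion 12, yet restart there is accepted. That is right for the enzyme. What separates the two cases is bilirubin. The SAP grades are for summarizing laboratory data and do not govern dosing; they indicate seriousness only.

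Third, the clause leaves the initial hold discretionary, so a participant never held could continue at values that would bar restart in one who was held. This also stands. It is a reason for the safety physicians to look at the whole tier, not a reason to leave the restart sentence as it is.

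A reader might infer that the above-8 × ULN tier has the same defect. The documents do not support that: its stop clause carries no period and can be read as already barring restart. Nor do they support reading the text as permission to restart at once for someone who enters at 3 to <5 × ULN with raised bilirubin, since there is then no fall from 5.0 × ULN to act on.

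**Conclusion.** The concern holds in a limited form and should be corrected. In the second tier, a participant whose AST/ALT has fallen from 5 × ULN or more to between 3 and <5 × ULN, with bilirubin still at least 2.0 × ULN, meets the restart wording while still meeting the tier's entry criterion. No rule in the documents sets a bilirubin limit for restart.

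The exposure runs until the mandatory stop applies, at about 4 weeks, and mainly concerns an immediate or short hold. This assumes that the 4 weeks count from onset of the abnormality, which the text does not say. A reader might infer open-ended re-dosing; the stop rule excludes that.

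A reader might also infer an equal gap in both groups, because study intervention covers bedaquiline and rifamycin. It is clearest for bedaquiline. For rifamycin, Section 6.4 also defers to local practice and labeling, which cannot be checked from these documents.

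The documents give no event rate. My judgement is that few of the 124 participants would be affected. The point concerns participant safety and does not challenge the efficacy analysis.

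**What to change.** In the second tier of Section 8.2.6, allow the single restart only if AST/ALT is <5.0 × ULN and the participant does not have AST/ALT ≥3.0 × ULN with bilirubin ≥2.0 × ULN. Add the same clause to the above-8 × ULN tier for consistency; it also removes the conflict there between the restart sentence and the stop clause. The thresholds are the protocol's own, and the clause gives a usable limit to participants who enter at 3 to <5 × ULN with raised bilirubin. A stricter bilirubin cut-off is for the sponsor's safety physicians.

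As optional clarifications, state when the 4 weeks begin and give a persistence period in the above-8 × ULN tier.

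The cost is one clause in each of two paragraphs. AST, ALT and bilirubin are already monitored in both tiers, so no tests are added. Some participants would stay off drug longer or stop altogether, and discontinuation before Week 24 counts as non-conversion under the primary estimand. With few participants likely to be affected, that is a small price.

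### Section 8.2.6 opens both upper liver tiers on AST or ALT, but its enzyme test for permanent discontinuation asks for AST and ALT, so one persistently raised enzyme with bilirubin below 2 x ULN meets no mandatory laboratory stop

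*Protocol*

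**What the plan says.** Protocol Section 8.2.6 sets the liver rules, and Section 7.1.1 (liver chemistry stopping criteria) only refers back to it. The scope line reads "For participants with AST and/or ALT elevations".

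- **Entry.** The middle tier covers 5.0 to 8.0 x ULN, or 3 x ULN with bilirubin at 2.0 x ULN or more. It opens on "AST or ALT elevation or" that bilirubin alternative. The top tier, above 8.0 x ULN, also opens on either enzyme.
- **Hold.** In the middle tier the first action is to stop the suspected background drug permanently or hold study intervention. If values do not improve, "the study intervention will be temporarily withheld for up to 2 weeks per investigator discretion". In the top tier, "Per investigator discretion, the study intervention will be temporarily withheld for up to 2 weeks".
- **Restart.** When AST/ALT falls below 5.0 x ULN, "study intervention can be restarted once" in the middle tier and "study intervention can be restarted one time" in the top tier.
- **Mandatory permanent stop.** Both tiers use the same three limbs for failure to improve. The first two are "no improvement in clinical course or persistent AST and ALT" at 5.0 x ULN or more. The third is AST/ALT at 3.0 x ULN or more together with bilirubin at 2.0 x ULN or more; the middle tier adds a 4-week period.

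Study intervention means bedaquiline and rifamycin (Protocol Section 2), so the rule covers both arms.

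**The concern.** The connective changes between entry and exit. One enzyme is enough to bring a participant under the rule, but the enzyme limb of the mandatory stop asks for two. The bilirubin limb in the same sentence uses a slash instead, so a careful site could infer that the difference is deliberate. Two sites could then act differently on the same result: one stops drug permanently, the other does not have to.

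A discordant pair is plausible for this drug. Section 2.2 describes bedaquiline's liver signal as a rise in AST with a smaller rise in ALT. A rule that needs both enzymes at 5 x ULN is least sensitive to that pattern. Participant safety is at stake, along with consistent application of a stated stopping rule.

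**Working it through.** This is a question of logic, so the check is to write the conditions out and run cases through them. Let A, L and B be AST, ALT and total bilirubin in multiples of ULN, with the clinical course not judged unimproved and the values persistent.

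**Conditions from Section 8.2.6**

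- Top tier entry: A > 8 or L > 8.
- Middle tier entry: A or L from 5 to 8, or max(A, L) ≥ 3 with B ≥ 2.
- Laboratory stop as written: (A ≥ 5 and L ≥ 5), or (max(A, L) ≥ 3 and B ≥ 2). The slash in the bilirubin limb is read as either enzyme.
- Laboratory stop with *or*: max(A, L) ≥ 5, or (max(A, L) ≥ 3 and B ≥ 2).

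**Cases**

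| A | L | B | Tier | Stop as written | Stop with *or* |
|---|---|---|---|---|---|
| 9 | 4 | 1 | above 8 | no | yes |
| 7 | 2 | 1 | 5 to 8 | no | yes |
| 2 | 7 | 1 | 5 to 8 | no | yes |
| 12 | 2 | 1 | above 8 | no | yes |
| 12 | 4.9 | 1.9 | above 8 | no | yes |
| 7 | 7 | 1 | 5 to 8 | yes | yes |
| 7 | 2 | 2.5 | 5 to 8 | yes | yes |
| 12 | 2 | 2 | above 8 | yes | yes |
| 4 | 1 | 2 | middle, by bilirubin | yes | yes |

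**The gap in general.** The two versions differ only when max(A, L) ≥ 5, min(A, L) < 5 and B < 2. If B ≥ 2, then max(A, L) ≥ 5 already satisfies the bilirubin limb. Nothing outside that region changes. In the first row, SAP Appendix 10 would grade the AST as Grade 4 and the ALT as Grade 3.

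The last three rows stop as written only if the slash means either enzyme. If it meant both, they would not stop.

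**Is there a laboratory stop elsewhere?**

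| Safeguard | Where | Why it does not close the gap |
|---|---|---|
| Stop suspected background drug or hold study intervention | 8.2.6, middle tier | Either action suffices; the hold is temporary |
| Hold of up to 2 weeks | 8.2.6, both tiers | At investigator discretion |
| Single restart, below 5.0 x ULN | 8.2.6, both tiers | Acts only once drug has been held |
| No restart after more than 30 days | Section 6.4, Table 3 | Bedaquiline only, and only if interrupted |
| Clinical course limb | 8.2.6, both tiers | Clinical judgement, not a laboratory value |
| Safety or tolerability judgement | Section 7.1 | No liver threshold |

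None is a mandatory laboratory stop for one raised enzyme with bilirubin below 2 x ULN.

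**The case against.** **Intent can be recovered.** The limbs illustrate failure to improve. The heading and scope line cover AST and/or ALT, and the same paragraph is loose with conjunctions elsewhere: "If ALT, AST, and bilirubin do not improve or worsens within 2 weeks". Many sites would read the stop as either enzyme. This makes the matter a wording correction, and divergent site behaviour is possible rather than shown. It does not make the text say what was probably intended.

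**The safeguards are substantial.** In the middle tier, discretion can be read as a choice between two actions rather than leave to do nothing. On the natural reading of the restart gate, a held participant whose AST stays at 9 x ULN cannot resume. With Table 3, a bedaquiline hold then becomes permanent after 30 days. Hepatitis work-up and follow-up to resolution or stabilization are also required. All of this stands. The gap therefore bites mainly when the investigator does not hold drug, does not judge the course unimproved and does not use Section 7.1.

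**The *and* might be deliberate.** Section 2.2 reports AST rises with skeletal-muscle toxicity in animals, and myalgia has its own stop in Section 8.2.6. Sparing AST of muscle origin would be defensible. But the protocol does not state that purpose, and a two-enzyme rule also misses isolated ALT.

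**Stronger readings that the documents do not support.** A reader might infer that a single raised enzyme can never meet a laboratory stop. It can, through the bilirubin limb, on the usual reading of the slash. A reader might also infer that such a participant goes on dosing unchecked; the safeguards above contradict that.

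**Conclusion.** The mismatch is real and appears in both tiers. Its size is the region worked out above: one enzyme persistently at or above 5 x ULN, the other below it, bilirubin below 2 x ULN, and a clinical course not judged unimproved. There, the literal text contains no mandatory laboratory stop, although several partial safeguards apply.

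This rests on reading *and* literally and the slash as either enzyme. The documents do not say how often persistent discordant values occur, so neither the number of participants affected nor any effect on power can be calculated. A power loss could be produced by assuming some number of extra stops, but it would reflect that assumption and would not measure the defect. A stated safety rule that fails when followed to the letter should be corrected, and the correction is small.

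**What to change.** In the permanent-stop sentence of both tiers, require discontinuation for persistent AST *or* ALT at 5.0 x ULN or more. If AST of muscle origin is to be spared, write that exception explicitly and tie it to CPK and CPK-MB, which are already in the Appendix 2 chemistry panel.

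Two optional clarifications would help: say that restart needs both enzymes below 5.0 x ULN, and that AST/ALT in the bilirubin limb means either enzyme.

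The cost is a protocol amendment with IEC/IRB approval (Section 10.3.1) and no new data collection. There may be a few more permanent stops in either arm. A stop before Week 24 counts as nonconversion under Protocol Section 9.4.2 and SAP Section 5.3.2. Each one moves that arm's rate by at most 1/62 = 1.6 percentage points at the planned size, and only if the participant would otherwise have converted. Stops that investigators would make anyway under Section 7.1 add nothing.
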